5.9. Treatment Guidelines

5.9.1. Re-treatment Criteria

5.9.1.1. To Begin a New Cycle of Treatment

In the absence of otherwise dose-limiting toxicity, for a patient to begin a new cycle of therapy, the following criteria must be met.

- ANC must be $\geq 1.5 \times 10^9 / L (1,500 / \mu L)$
- Platelet count must be $\geq 75 \times 10^9/L (75,000/\mu L)$
- All non-hematologic toxicities for which a causal association to study treatment cannot be ruled out, must be ≤ Grade 2 (except alopecia) or returned to baseline; the exception to this rule is treatment-emergent ocular symptoms, which must have recovered to < Grade 1 or baseline

If the patient does not meet these criteria, dosing will be delayed and the patient should be reevaluated within 48-72 hours. Dosing may resume if these criteria have been met. However, if the next cycle is delayed by greater than 14 days because of insufficient recovery from a treatment-related toxicity, this will be viewed as a dose-limiting event (Section 4.1.4). For patients treated on either dosing schedule, if the next cycle is delayed due to treatment-related toxicity by greater than 21 days then the patient should be removed from study treatment. In such cases, continuation of study treatment may be considered for those patients who have experienced clinical benefit if agreed upon between the Sponsor and the Investigator.

The use of granulocyte growth factors in accordance with ASCO guidelines may be implemented at the discretion of the treating physician after Cycle 1.

ImmunoGen, Inc. Confidential Page 74 of 138

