5.9.3. Criteria for Re-Initiation of Study Treatment Following Occurrence of a DLT

Study treatment will be stopped if a patient experiences a DLT at any time during the study. It may resume, with applicable dose adjustments (Section 5.9.4.1) if the following criteria are met:

- ANC must be $\ge 1.5 \times 10^9 / L (1500 / \mu L)$
- Platelet count must be $\geq 75 \times 10^9/L (75,000/\mu L)$
- All clinically-significant non-hematologic toxicities for which a causal association to study treatment cannot be ruled out must be ≤ Grade 1 (except alopecia) or returned to baseline

ImmunoGen, Inc. Confidential Page 75 of 138

If the patient does not meet these criteria, dosing will be delayed and the patient should be reevaluated within 48-72 hours. Dosing may resume if these criteria have been met. However, if the next cycle is delayed by greater than 14 days because of insufficient recovery from a treatment-related toxicity, this may be viewed as a dose-limiting event (Section 4.1.4). For patients treated on either schedule, if the next cycle is delayed due to treatment-related toxicity by greater than 21 days then the patient should be removed from study treatment. In such cases, continuation of study treatment may be considered for those patients who have experienced clinical benefit if agreed upon between the Sponsor and the Investigator.

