10.3. Cycle 2 Assessments

10.3.1. Cycle 2, Day 1

- Confirm that the patient satisfies all retreatment criteria (Section 5.9.3)
- Symptom-directed physical exam (Appendix A and Appendix B)

ImmunoGen, Inc. Confidential Page 98 of 138

- Vital signs (Section 8.6, Appendix A and Appendix B)
- Pulse oximetry (Section 8.8)
- Weight (Appendix A and Appendix B)
- ECOG performance status (Appendix A and Appendix B)
- Clinical laboratory tests (Section 8.10, Appendix A and Appendix B)
 - o Serum chemistry
 - Hematology
 - Coagulation profile
 - Urinalysis
- Directed neurological examination will be performed, to include light touch, pinprick, proprioception, and deep tendon reflexes (DTRs) of the upper and lower extremities; and questioning for symptoms of paresthesia and numbness. (Appendix A and Appendix B)
 - o Neurotoxicity Questionnaire (FACT/GOG NTx), Version 4.0 (Appendix G)
- IMGN853 administration (Appendix A and Appendix B)
- AEs and SAEs (Appendix A and Appendix B)
- Ocular symptom assessment (Section 5.8.8)
- Concomitant medications
- PK sample collection, as outlined in Section 6 and Appendix C
- HAHA and HADA sample collection as outlined in Section 6 and Appendix C

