10.6. Cycles \geq 4 Assessments

10.6.1. Cycles ≥4, Day 1

Within 96 hours prior to Day 1:

- Confirm patient meets retreatment criteria as outlined in Section 5.9.3.
- Symptom-directed physical examination (Appendix A and Appendix B)
- Vital signs (Section 8.6, Appendix A and Appendix B)
- Pulse oximetry (Section 8.8)
- Weight (Appendix A and Appendix B)
- ECOG performance status (Appendix A and Appendix B)
- Clinical laboratory tests (Appendix A and Appendix B):
 - Serum chemistry
 - Hematology
 - Coagulation profile
 - Urinalysis
- Directed neurological examination will be performed, to include light touch, pinprick, proprioception, and deep tendon reflexes (DTRs) of the upper and lower extremities; and questioning for symptoms of paresthesia and numbness. If abnormal, an NCI CTAE grade will be recorded and if warranted a neurologist will be consulted (Appendix A and Appendix B)
 - o Neurotoxicity Questionnaire (FACT/GOG NTx), Version 4.0 (Appendix G)
- IMGN853 administration (Appendix A and Appendix B)
- AEs and SAEs (Appendix A and Appendix B)
- Ocular symptom assessment (Section 5.8.8)
- Concomitant medications (Appendix A and Appendix B)
- Up to Cycle 6 PK sample collection as outlined in Section 6 and Appendix C
- HAHA and HADA sample collection as outlined in Section 6 and Appendix C

ImmunoGen, Inc. Confidential Page 102 of 138

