APPENDIX A. SCHEDULE OF CLINICAL ASSESSMENTS –SCHEDULE A (Q3W)

			Cycle 1			Cycle	e 2		Cycle	3	Cycles ≥4	End of	28-Day
Activity	Screening	Day 1	Day 2	Day 8&15	Day 1	Day 8&15	Day 18±3	Day 1	Day 2	Day 8&15	Day 1	Treatment	Follow-up (+14 Days)
Informed consent	•a												
Demography	•a												
Medical History	● ^a												
Confirm Disease Diagnosis/Current Stage and Prognostic Index Evaluation	●a												
Record Baseline Signs and Symptoms	•	•											
Review and document IC/EC (Sections 3.1 and 3.1.2)	•c												
Confirm patient continues to satisfy I/E Criteria (Sections 3.1 and 3.1.2)		•											
Confirm patient meets retreatment criteria (Section 5.9.3)					•			•			•		
Height	● ^a												
Physical Examination ^b	• c	•		•	•	•		•			•	•	•
Weight	● ^c	•			•			•			•	•	•
Vital signs ^d	● ^c	•	•		•			•	•		•	•	•
Pulse oximetry		•	•	•	•	•		•	•	•	•	•	•
Pulmonary Function Test ^e	•												
ECOG PS	• c	•			•			•			•	•	•

			Cycle 1			Cycle	e 2		Cycle	3	Cycles ≥4	End of	28-Day
Activity	Screening	Day 1	Day 2	Day 8&15	Day 1	Day 8&15	Day 18±3	Day 1	Day 2	Day 8&15	Day 1	Treatment	Follow-up (+14 Days)
Hematology and Chemistry	● c	$ullet^{\mathrm{f}}$		•	•	•		•		•	•	•	•
Coagulation (PT/INR/aPTT)	• c	• f			•			•			•		•
Urinalysis	•c	● ^f			•			•			•		•
Pregnancy Test (urine or Serum) ^g	• c	•					Even- numbered cycles (2, 4, 6, etc.) ^g						•g
Ophthalmic examinationsh	•						Every other cycle (from point at which toxicity first reported)h					•	•
Schirmer Test ^h	•						-emergent eye mic examinati indicated						
Ocular Symptom Assessment ^h		•			•			•			•	•	•
Radiologic tumor assessments	● ^a						Every 6 weeks ± 1 week) ⁱ					•j	•j
CA125 (Appendix F)	• c						Every 6 weeks(± 1 week) ⁱ					•j	•j
12-Lead ECG (Section 8.7) ^k	●c	•	•					•	•			•	•1

			Cycle 1			Cycle	e 2		Cycle	3	Cycles ≥4	End of	28-Day
Activity	Screening	Day 1	Day 2	Day 8&15	Day 1	Day 8&15	Day 18±3	Day 1	Day 2	Day 8&15	Day 1	Treatment	Follow-up (+14 Days)
Neuropathy assessment, including FACT/GOG- Neurotoxicity Questionnaire	● c	•			•			•			•		•
IMGN853 Infusion		•			•			•			•		
Corticosteroid Eye Drops		Patients in Expansion Cohort 5 (only) will self-administer corticosteroid eye drops as described in Section 5.8.2											
Lubricating Eye Drops		Α	ll patier	nts will s	elf-adm	inister lu	bricating eye	drops a	as descri	bed in Sec	tion 5.8.3		
AE and SAE assessments	● ⁿ	•		•	•	•		•	•	•	•	•	•
Record concomitant medications	● c	•		•	•	•		•	•	•	•	•	•

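### Every Day 1 retreatment check cites the post-DLT restart section (5.9.3) instead of the new-cycle section (5.9.1.1), and two appendix footnotes stop dosing for any ocular symptom, against Table 8

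*Protocol*

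**What the plan says.** The Day 1 check appears five times. Sections 10.3.1 (Cycle 2) and 10.4.1 (Cycle 3) both read "Confirm that the patient satisfies all retreatment criteria (Section 5.9.3". Section 10.6.1 (Cycle 4 onward) reads "Confirm patient meets retreatment criteria as outlined in Section 5.9.3". The schedule tables in Appendices A and B each carry the row "Confirm patient meets retreatment criteria (Section 5.9.3".

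Section 5.9.1.1 covers the ordinary start of a cycle: "In the absence of otherwise dose-limiting toxicity, for a patient to begin a new cycle of therapy, the following criteria must be met". Its limit for related non-hematologic toxicity is "must be ≤ Grade 2 (except alopecia) or returned to baseline", with a stricter limit for ocular symptoms.

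Section 5.9.3 is headed as the criteria for re-initiation after a DLT. It requires: "All clinically-significant non-hematologic toxicities for which a causal association to study treatment cannot be ruled out must be ≤ Grade 1 (except alopecia". If the next cycle slips by more than 14 days, "this may be viewed as a dose-limiting event (Section 4.1.4" applies. If it is delayed "by greater than 21 days then the patient should be removed from study treatment", subject to an exception for clinical benefit agreed between Sponsor and Investigator.

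On the eye, Appendix A footnote h and Appendix B footnote g say that IMGN853 is stopped if the patient reports ocular symptoms, with no grade threshold, and refer to Section 5.8.8. Within that section, 5.8.8.1 refers patients for examination at any grade but interrupts treatment only from Grade 2, and Table 8 continues dosing at Grade 1.

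**The concern.** The Day 1 check decides whether a patient is dosed, and it sends the site to the wrong rule. The two sections differ for one identifiable group: patients without a DLT who have related, clinically significant, non-ocular Grade 2 toxicity above baseline. The protocol means to dose them, and the cited section would hold them.

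The situation is foreseeable. Section 5.8.10 reports mild to moderate diarrhea as common, and moderate corresponds to Grade 2 in Table 14.

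A wrong hold delays dosing. Section 5.9.4.1 allows a patient whose drug was held for an adverse event to resume at a reduced dose. A delay over 14 days may be classed as dose-limiting, and Table 5 lists failure to meet retreatment criteria in time as a DLT. Past 21 days the default is removal from treatment. The choice of section can therefore reach exposure, dose and event classification.

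The footnotes raise the same issue for ocular symptoms. A patient with Grade 1 symptoms would have a dose stopped that Table 8 continues. Footnote h matters for all Schedule A patients; footnote g matters only for those still on Schedule B.

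**Working it through.** **Step 1: count the pointers.** Sections 10.3.1, 10.4.1 and 10.6.1, the Appendix A row and the Appendix B row give 5 of 5 citing 5.9.3 and 0 of 5 citing 5.9.1.1. Section 4.1.4 also cites 5.9.3, but correctly, because it concerns resuming after a DLT.

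**Step 2: compare the two sections.**

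| Item | 5.9.1.1 (new cycle) | 5.9.3 (after a DLT) |
|---|---|---|
| ANC | at least 1.5 x 10^9/L | the same |
| Platelets | at least 75 x 10^9/L | the same |
| Related non-hematologic toxicity | Grade 2 or lower, or baseline; stricter for ocular | Grade 1 or lower, or baseline, if clinically significant |
| Delay over 14 days | will count as dose-limiting | may count as dose-limiting |
| Delay over 21 days | remove, unless continuation is agreed for clinical benefit | the same |

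The blood-count limits cannot produce a different decision. The non-hematologic limit can. Grade 2 pneumonitis is not an example, because Table 9 holds it anyway.

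**Step 3: compare the ocular rules.** Footnotes h and g stop at any symptom. Section 5.8.8.1 and Table 8 continue at Grade 1 and hold from Grade 2. Both footnotes conflict with the section they cite.

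**Step 4: illustrate one wrong hold.** The documents do not say how often one would occur. The hold lengths below are assumptions: 3 days is the logistics allowance in 5.7.1.1, and 14 and 21 days are the limits in 5.9.1.1 and 5.9.3. By SAP 6.1 for Schedule A, weeks = (last dose date - first dose date + 21)/7, dose intensity = total dose/(AIBW x weeks/3), and relative dose intensity (RDI) = dose intensity/6.

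With k doses, one hold of h days, and D the sum of doses in mg/kg, weeks = (21k + h)/7, so RDI = (D/6) x 21/(21k + h).

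If every dose stays at 6 mg/kg, D = 6k and RDI = 21k/(21k + h):

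- k = 2: 42/45 = 93.3% (3 days), 42/56 = 75.0% (14 days), 42/63 = 66.7% (21 days).
- k = 6: 126/129 = 97.7%, 126/140 = 90.0%, 126/147 = 85.7%.

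A 21-day delay exceeds 14 days. If it is classed as a DLT, 4.1.4 requires a lower dose on resumption, which Table 11 sets at 5.0 mg/kg:

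- k = 2: D = 6 + 5 = 11; (11/6) x 21/63 = 61.1%.
- k = 6, hold before dose 2: D = 6 + 5 x 5 = 31; (31/6) x 21/147 = 73.8%.
- k = 6, hold before dose 6: D = 5 x 6 + 5 = 35; (35/6) x 21/147 = 83.3%.

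The 21-day range is therefore 61-67% after two doses and 74-86% after six. The 3-day and 14-day figures would also be lower if the investigator used the reduction that 5.9.4.1 permits.

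**Step 5: eye drops, an editorial mismatch.** Sections 4.1.5 and 3.1.F.f and the synopsis imply 4 x 10 = 40 administrations per cycle. Section 5.8.2 and Table 7 footnote 5 give 6 x 5 + 4 x 5 = 50.

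**The case against.** The strongest reply is that 5.9.3 limits its own scope. Its heading and opening sentence concern patients who have had a DLT, so read literally it sets no condition for anyone else, and 5.9.1.1 plainly governs a new cycle. A careful site would notice. This lowers the chance of a wrong hold. It does not make the instruction right: on that reading the Day 1 check points to criteria that do not apply and is left empty.

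A wrong hold also needs the toxicity to be judged clinically significant and to persist to the next Day 1. Section 5.8.10 says that moderate diarrhea is common, not that it persists. That stands, and is why no frequency is given.

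For the footnotes, stopping and then referring could be read as a pause pending examination. Even so, Table 8 provides no pause at Grade 1.

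The eye-drop mismatch has little operational effect. Section 5.8.2 and Table 7 footnote 5 give the intended regimen, Appendix A refers to 5.8.2, and two of the three discrepant statements are eligibility wording. A reader might infer that Cohort 5 was treated with the wrong regimen; the documents do not support that.

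**Conclusion.** The five pointers are wrong as written, and both ocular footnotes contradict the rules they cite. These are operative dosing thresholds, so the point is more than typographical, but it is minor. No primary endpoint, sample size or planned analysis is shown to be affected.

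The size in patients cannot be computed. The dose-intensity figures show what one hold does under assumed lengths and, at 21 days, with or without a dose reduction. A 3-day hold is no longer than the logistics delay already allowed.

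A reader might go further and infer that the pointers distorted the MTD, the Cycle 1 DLT counts or the 33% enrollment stop in the expansion cohorts. The documents do not support that: they do not show that any site applied 5.9.3 to a patient without a DLT, and 5.9.3 only says that a long delay may be dose-limiting. Nor can one say that a wrong hold never leads to a lower dose. Table 8 lets Grade 2 ocular events resume at the same dose when the delay is 14 days or less, but 5.9.4.1 permits a reduction after a hold for an adverse event.

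The ocular limit in 5.9.1.1 prints here as below Grade 1. Section 5.9.1.2 and Table 8 both accept Grade 1, so Grade 1 or lower appears intended, and the symbol may be a reading error. The conclusion does not depend on it.

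**What to change.** 1. Cite 5.9.1.1 in 10.3.1, 10.4.1, 10.6.1 and the Appendix A and B rows, and state that the event-specific holds in Tables 8 and 9 still apply.
2. Confirm that the ocular limit in 5.9.1.1 is Grade 1 or lower. If it really is below Grade 1, correcting the pointers alone would bring in a new conflict with Table 8.
3. Keep 5.9.3 for restart after a DLT, as in 4.1.4, and reconcile it with 5.9.4.2. That section carries the same heading but different criteria (recovery within 14 days, clear clinical benefit and a favorable risk/benefit profile), and 5.9.4.1 points to it. Otherwise two post-DLT rules remain.
4. Reword Appendix A footnote h and Appendix B footnote g: refer for ophthalmic examination at any grade, and hold from Grade 2 according to Table 8.
5. As editorial alignment only, match the eye-drop frequency in 4.1.5, 3.1.F.f and the synopsis to 5.8.2.

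The cost is a text-only protocol clarification with no SAP change, extra patients or procedures. Under Section 13.9 it still needs written IRB/IEC approval and submission to the regulatory authorities, and could be carried in the next amendment.

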10.3.2. Cycle 2, Day 8±3 Days

- Blood sample for measurement of homocysteine and methylmalonate as outlined in Section 7.2.3 and Appendix C
- Fresh tumor biopsy Expansion Cohort #3 (Sections 7.1.1, 7.3.1 and Appendix C)
 - In addition, patients who relapse after showing clinical benefit will be asked to undergo an optional biopsy at the time of disease progression to help understand the mechanism of resistance to IMGN853

10.3.3. Cycle 2, Day 8 and 15

- Symptom-directed physical examination
- Vital signs (Section 8.6, Appendix A and Appendix B)
- Clinical laboratory tests (Section 8.10, Appendix A and Appendix B):
 - o Serum chemistry
 - Hematology

ImmunoGen, Inc. Confidential Page 99 of 138

- Pulse oximetry (Section 8.8)
- AEs and SAEs (Appendix A and Appendix B)
- Concomitant medications (Appendix A and Appendix B)
- Schedule B Only: IMGN853 administration (Appendix A and Appendix B) Cycle 3
 Assessments

10.4. Cycle 3 Assessments

10.4.1. Cycle 3, Day 1

- Confirm that the patient satisfies all retreatment criteria (Section 5.9.3)
- Symptom-directed physical examination (Appendix A and Appendix B)
- Vital signs as outlined in Section 8.6, Appendix A and Appendix B
- Pulse oximetry (Section 8.8)
- Weight (Appendix A and Appendix B)
- ECOG performance status (Appendix A and Appendix B)
- Clinical laboratory tests (Section 8.10, Appendix A and Appendix B):
 - Serum chemistry
 - Hematology
 - Coagulation profile
 - o Urinalysis
- ECG performed in triplicate as outlined in Section 8.7.
- Directed neurological examination will be performed, to include light touch, pinprick, proprioception, and deep tendon reflexes (DTRs) of the upper and lower extremities; and questioning for symptoms of paresthesia and numbness (Appendix A and Appendix B).
 - o Neurotoxicity Questionnaire (FACT/GOG NTx), Version 4.0 (Appendix G)
- IMGN853 administration
- AEs and SAEs (Appendix A and Appendix B)
- Ocular symptom assessment (Section 5.8.8)
- Concomitant medications
- PK sample collection as outlined in Section 6 and Appendix C
- HAHA and HADA sample collection as outlined in Section 6

10.4.2. Cycle 3, Day 2

• PK sample collection as outlined in Section 6 and Appendix C

ImmunoGen, Inc. Confidential Page 100 of 138

- ECG performed in triplicate as outlined in Section 8.7
- Vital signs as outlined in Section 8.6, Appendix A and Appendix B
- Pulse oximetry (Section 8.8)
- AEs and SAEs (Appendix A and Appendix B)
- Concomitant medications

10.4.3. Cycle 3, Day 3 and Day 4 or 5 (Schedule A Only)

• PK sample collection as outlined in Section 6 and Appendix C

10.4.4. Cycle 3, Day 8 and 15

- Clinical laboratory tests:
 - o Serum chemistry
 - Hematology
- Pulse oximetry (Section 8.8)
- AEs and SAEs (Appendix A and Appendix B)
- Concomitant medications
- Schedule B Only:
 - o IMGN853 administration (Appendix A and Appendix B)
 - o PK sample collection as outlined in Section 6 and Appendix C

10.4.5. Cycle 3, Day 16 (Schedule B only)

• PK sample collection as outlined in Section 6 and Appendix C

10.4.6. Cycle 3, Day 22 (Schedule B only)

• PK sample collection as outlined in Section 6 and Appendix C

10.5. Even-Numbered Cycles (2, 4, 6, etc.), End of Cycle

- Pregnancy test (may be performed more frequently in accordance to institutional requirements) (Appendix A and Appendix B)
 - o **Schedule A** − Day 18±3 days
 - Schedule B Day 21±3 days
- For patients who experience ocular toxicity and those who experience blurred vision but have normal eye examinations: complete ophthalmic examination (Section 5.8.8); to be performed by a board-certified ophthalmologist prior to the start of every other cycle from the time it is first reported.
- Tumor assessments by CT scan (Appendix A and Appendix B)
 - **Schedule A** Every 6 weeks±1 week

- o **Schedule B** − Every 8 weeks±1 week
- CA125 for patients with EOC, primary peritoneal cancer, fallopian tube cancer or uterine cancer (Appendix F) should be scheduled to coincide approximately with the radiographic tumor assessments

NOTE: Patients experiencing CA125 response must have a confirmatory test performed 28 days after initial response is documented.

10.6. Cycles \geq 4 Assessments

10.6.1. Cycles ≥4, Day 1

Within 96 hours prior to Day 1:

- Confirm patient meets retreatment criteria as outlined in Section 5.9.3.
- Symptom-directed physical examination (Appendix A and Appendix B)
- Vital signs (Section 8.6, Appendix A and Appendix B)
- Pulse oximetry (Section 8.8)
- Weight (Appendix A and Appendix B)
- ECOG performance status (Appendix A and Appendix B)
- Clinical laboratory tests (Appendix A and Appendix B):
 - Serum chemistry
 - Hematology
 - Coagulation profile
 - Urinalysis
- Directed neurological examination will be performed, to include light touch, pinprick, proprioception, and deep tendon reflexes (DTRs) of the upper and lower extremities; and questioning for symptoms of paresthesia and numbness. If abnormal, an NCI CTAE grade will be recorded and if warranted a neurologist will be consulted (Appendix A and Appendix B)
 - o Neurotoxicity Questionnaire (FACT/GOG NTx), Version 4.0 (Appendix G)
- IMGN853 administration (Appendix A and Appendix B)
- AEs and SAEs (Appendix A and Appendix B)
- Ocular symptom assessment (Section 5.8.8)
- Concomitant medications (Appendix A and Appendix B)
- Up to Cycle 6 PK sample collection as outlined in Section 6 and Appendix C
- HAHA and HADA sample collection as outlined in Section 6 and Appendix C

ImmunoGen, Inc. Confidential Page 102 of 138

10.6.2. Cycles \geq 4, Day 8 and 15 (Schedule B)

- Clinical laboratory tests (Section 8.10, Appendix A and Appendix B):
 - Serum chemistry
 - Hematology
- Pulse oximetry (Section 8.8)
- Concomitant medications (Appendix A and Appendix B)
- IMGN853 administration (Appendix A and Appendix B)
- AEs and SAEs (Appendix A and Appendix B)

10.7. End of Treatment Visit

Patients may voluntarily withdraw from the study treatment at any time for any reason, and without prejudice to further treatment. In addition, patients may be withdrawn by the Investigator if they do not feel the patient is deriving clinical benefit or because the patient is experiencing unacceptable toxicity. The reasons for which a patient may be prematurely discontinued are listed in Section 5.10.

Patients who withdraw or are removed from the study treatment will have an end of treatment visit within 7 days of the decision to discontinue study treatment. All study evaluations described below will be performed. Additionally, these patients will undergo a 28-day follow-up safety visit. The eCRF will capture reasons for withdrawal.

The procedures listed below are to be undertaken at the end of treatment visit and documented in the eCRF:

- Symptom-directed physical examination (Appendix A and Appendix B)
- Vital signs as outlined in Section 8.6, Appendix A and Appendix B
- Pulse oximetry (Section 8.8) Weight (Appendix A and Appendix B)
- ECOG performance status (Appendix A and Appendix B)
- Clinical laboratory tests (Section 8.10, Appendix A and Appendix B):
 - Serum chemistry
 - Hematology
- Blood sample for measurement of homocysteine and methylmalonate as outlined in Section 7.2.3 and Appendix C
 - Ophthalmic examinations: visual acuity, fundoscopic exam, ocular symptom assessment (Section 5.8.8)
 - Single, 12-lead ECG (Section 8.7)
 - Radiologic imaging to monitor tumor response if PD has not been documented already (Appendix A and Appendix B)

ImmunoGen, Inc. Confidential Page 103 of 138

 CA125 - for patients with EOC, primary peritoneal cancer, fallopian tube cancer or uterine cancer (Appendix F)

NOTE: patients experiencing CA125 response must have a confirmatory test performed at least 28 days after initial response is documented.

- AEs and SAEs (Appendix A and Appendix B)
- Ocular symptom assessment (Section 5.8.8)
- Concomitant medications (Appendix A)
- HAHA and HADA sample collection as outlined in Section 6 and Appendix C

